10.6 Urine PK Parameters MAD

All PK summary tables and figures will be based on the PK population. All analyses will be summarized as described in [section 3.1](#) (PK - continuous descriptive analysis). All listings will be based on the safety population. All missing and BLQ handling of urine concentrations for PK analysis will be based on section 3.5.

Pharmacokinetic analysis will be carried out using actual doses, actual urine sampling times (start and end times), actual urine volumes, where possible. If actual times are missing, nominal times may be used

with sponsor approval. The following urine pharmacokinetic parameters will, where possible, be determined from the urine concentrations of CVN766 and the respective urine volumes within each collection interval by non-compartmental method using Phoenix WinNonlin software (Version 8.3 or higher, Certara, USA):

Note: PK urine samples and urine volumes will be collected at the following timepoints (± 15 minutes) on Day 1: 0 to 6, 6 to 12, and 12 to 24 hours post dose for MAD and on Days 7: 0 to 6, 6 to 12 and 12 to 24 hours for MAD Cohort 1.

PK concentration and parameter data will be analyzed descriptively as noted in [section 3.1](#).

General Urine NCA Pharmacokinetic Settings

The general settings in Phoenix WinNonlin® for generation of urine PK parameters are as listed below.

- NCA Model Type: Urine (210-212)
- Weighting: Uniform
- AUC Calculation Method (if applicable): Linear trapezoidal/ linear interpolation method

10.7 Criteria for the Calculation of an Apparent Terminal Elimination Half-Life

The start of the terminal elimination phase for each participant will be defined by visual inspection and will generally be the first point at which there is no systematic deviation from the log linear decline in plasma concentrations.

Number of Data Points

At least 3 data points will be included in the regression analysis and not including C_{max} . The number of points and the beginning and end times of the terminal phase will be listed for each individual.

Plausibility

The data will be pharmacokinetically plausible.

Summary of Plasma / Urine PK Concentrations and PK Parameters

Plasma PK (concentration and PK parameters $Ae_{t-0.5}$, $Fe_{t-0.5}$, and CL_r) data for Part 1 (SAD) and Part 2 (MAD) will be summarized separately. All PK summary tables and figures will be based on the PK population, and PK listings will be based on PK population. All analyses will be summarized descriptively in general according to section 3.1

The actual blood sampling dates and times relative to dosing time will be listed by participant and nominal sampling time, with time deviation calculated, for all participants with available plasma concentration data, including participants excluded from the PK population. Individual values for PK concentration data will be reported to the same level of precision as received from the bioanalytical laboratory.

Summary of PK concentrations

For the concentration-time data/profile summary, the following will be applied:

- For the concentration descriptive summaries, concentrations may be excluded if sampling time deviation is considered too large to affect the profile at the discretion of the pharmacokineticist.
- Concentrations that are below limit of quantification (BLQ) will be set to 0 for the calculation of standard statistics (i.e. arithmetic mean) and set to missing for the calculation of geometric statistics. For PK parameters, all plasma concentrations will be set to BLQ if prior to first measurable concentration and treated as missing thereafter

Individual (for each participant) and mean (SD) concentrations over time for the analyte will be displayed graphically in linear and semi-logarithmic plots of the analyte concentrations versus time. The actual collection time will be used for individual plasma analyte concentration curves, and the nominal time will be used for the plots of mean plasma analyte concentration curves.

Summary of Plasma PK parameters

PK parameters will be determined for each analyte with intensive PK samplings. For the purpose of calculating the non-compartmental PK parameters, concentrations that are BLQ prior to the first measurable concentration value will be set equal to zero. BLQ values embedded between measurable concentrations will be set to missing. Concentrations that are BLQ in the terminal phase after the last measurable concentration will be set to missing.

It should be noted the imputation of BLQ for the determination of PK parameters is different from the BLQ imputation when PK concentrations are summarized. When PK parameters are estimated by a standard non-compartmental model, actual collection time will be used in the calculation of plasma PK parameters.

Goodness of Fit

- If data permits, the default ‘best fit’ method by Phoenix WinNonlin will be used for the selection of slopes to determine ‘ λ_z ’. If data do not permit, then the slope selection will be done by visual inspection or by a manual method to determine λ_z .
- When assessing terminal elimination phases, the R^2 adjusted value will be used as a measure of the goodness of fit of the data points to the determined line.
- Regression-based parameters (λ_z or k_{el} , AUC_{inf} , $AUC\%_{extrap}$, $t_{1/2}$, CL/F or CL/Fss, and V_z/F or V_z/F_{ss}) will only be calculated if the R^2 adjusted value of the regression line is greater than or equal to 0.8. If regression-based parameters cannot be calculated, they will be set to “NC”, defined as “not calculated” in the data listings and summary tables as appropriate.

Calculation of AUC

- The minimum requirement for the calculation of AUC will be the inclusion of at least 3 consecutive plasma concentrations above the lower limit of quantification (LLOQ), with at least one of these concentrations following C_{max} .
- All AUC values will be calculated using linear trapezoidal/ linear interpolation method

Period of Estimation

- Time period used for the estimation of $t_{1/2}$, where possible, will be over at least 2 half lives.
- Where an elimination half-life is estimated over a time period of less than 2 half-lives, it will be flagged in the data listings at the discretion of the pharmacokineticist, and the robustness of the half-life value and regression-based parameters (λ_z or k_{el} , AUC_{inf} , $AUC_{\%extrap}$, $t_{1/2}$, CL/F or CL/F_{ss} , and V_z/F or V_z/F_{ss}) should be discussed in the study report.

Inferential Analyses

The following endpoints will be analyzed as described in [sections 3.3](#):

- Dose proportionality
 - Dose proportionality - CVN766 SAD
 - AUC_{inf}
 - AUC_t
 - AUC_{24}
 - C_{max}
 - Dose proportionality - CVN766 MAD
 - MAD Day 1: C_{max} , AUC_{24}
 - MAD Day 7: $C_{max,ss}$, AUC_{tau}

- Food-Effect Assessment (SAD: Cohort S3):

The following parameters will be analyzed as described in [sections 3.3](#):

- AUC_t
- AUC_{inf}
- AUC_{24}
- C_{max}

- Gender effect Assessment

The following parameters will be analyzed as described in [sections 3.3](#):

SAD : $C_{max}/Dose$, $AUC_{24}/Dose$, $AUC_t/Dose$, $AUC_{inf}/Dose$, T_{max} and $t_{1/2z}$.

MAD Day 1: $AUC_{24}/Dose$, $C_{max}/Dose$, $AUC_t/Dose$, $t_{1/2z}$ and t_{max} .

MAD Day 7: $C_{max,ss}/Dose$, $AUC_{tau}/Dose$, $AUC_t/Dose$, $t_{1/2z}$ and t_{max} .

Details are provided in [section 3.3](#) of SAP.

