2.1.1 Part 1: SAD is the single-dose regimen and Fasted- Fed Crossover

Approximately 40 healthy male or female subjects will be enrolled in 1 of 5 single-dose cohorts (designated as S1 through S5, respectively) in an ascending fashion. An optional Cohort 3a may be added in parallel to SC3 for additional safety and tolerability evaluation. Cohort S3a dose level will be consistent with Cohort S3 (45 mg planned) in a fasted condition only and without lumbar puncture, aligned with other SAD cohorts. Each cohort will consist of 8 subjects randomized to CVN766 or placebo, whereby 6 subjects will receive a single oral dose of CVN766 suspension, and 2 subjects will receive a matching placebo suspension under overnight fasted conditions. Sentinel dosing (1 subject to receive CVN766 and 1 subject to receive placebo) will be used in each cohort to ensure adequate safety and tolerability evaluation prior to administering CVN766 or placebo to the remainder of the subjects within the cohort. The planned dose levels will be 5, 15, 45, 125, and 250 mg CVN766. Each following dose level may be higher, lower, or remain the same as the preceding cohort. Additional cohort(s) may be added if deemed necessary by the SRG to fully characterize the safety and tolerability of CVN766. To assess the effect of food on CVN766 bioavailability in suspension formulation, the single-dose administration will be repeated in a single cohort (S3) after ingestion of a standardized high-fat, high-calorie meal. Once the safety of the S3 cohort dose level has been assessed, the S3 cohort subjects will return to the clinic (no sooner than 14 days after their prior dose, or at least 4 half-lives, has lapsed based on preliminary PK data, whichever is longer). They will receive the same dose as before, administered after ingesting a standardized breakfast. Subjects will finish at least approximately 85% of their breakfast within 30 minutes and receive an investigational product 30 minutes (\pm 5 minutes) after beginning the meal. Sentinel dosing will not be required for subjects returning to the clinic for the fed regimen. If the CVN766 PK parameters in the fasted S3 cohort reveal poor absorption with inconclusive results, the fed cohort will be deferred until a higher dose level.

[figure not shown]
On Day 1, subjects will undergo safety monitoring and PK sampling from blood plasma through 72 hours post-dose and, for cohort S3 (fasted) only, from CSF via lumbar puncture at 3 hours post-dose

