2.1.2 Part 2 MAD is a Multiple-Dose Regimen

Approximately 24 healthy male and female subjects aged 18 to 55 will be enrolled in 1 of the 3 multiple-dose cohorts (designated as M1 through M3, respectively) in an ascending fashion. The dose levels planned to be studied in the multiple-dose regimen are 45, 125, and 250 mg CVN766 for multiple-dose cohorts M1 through M3, respectively. Each multiple-dose cohort will consist of 8 subjects randomized to CVN766 or placebo, whereby 6 subjects will receive a daily oral dose of CVN766, and 2 subjects will receive matching placebo for 7 days. Dosing will be administered in the fasting state; the SRG can change this if exposure is higher in the fed state. The planned dosing duration for the multiple-dose cohorts is 7 days. However, the duration may be increased to \leq 14 days if preliminary PK data suggest steady-state will not be achieved within 6 days of daily dosing.

On Day 1 subjects, will undergo safety monitoring and PK sampling from blood plasma through 24 hours post-dose and on Day 7, will undergo safety monitoring and PK sampling from blood plasma through 72 hours post-dose. Additionally, PK samples will be collected on Days 3, 4, 5 and 6 prior to the next planned dose. For cohort M1, on day 7 only, subjects will undergo PK sampling from CSF via lumbar puncture at 3 hours post dose and PK sampling from urine over 24 h on Day 1 and Day 7. CSF samples may also be taken from M2 and M3 cohorts at the SRG's discretion.

Figure 1: Study Design

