3.5 Handling of Missing Data

For the classification of Treatment emergent adverse event (TEAE), Medical History and Concomitant medication, the following will be applied in the following order:

- If all dates/times (start and stop) missing, the event/medication will automatically be classified as a TEAE/Concomitant medication.
- For AEs with a missing start date/time, if the event end date/time is prior to first study drug administration, the event will not be classified as a TEAE.
- If only the AE start year/ medication end year is present and is the same or is after the first study drug administration year unit, the event/medication will be classified as a TEAE/Concomitant medication.
- If the AE start month and year/medication end month and year are present and are the same or after the first study drug administration month and year units, the event/medication will be classified as a TEAE/Concomitant medication.
- If start AEs, Concomitant Medication and Medical History Day is missing, it will be assigned as 1st Day of the Month. If AEs, Concomitant Medication and Medical History Month is missing, it will be assigned as 1st Month of the Year and if AEs, Concomitant Medication and Medical History Year is missing, Informed Consent Year will be used.
- If end AEs, Concomitant Medication and Medical History Day is missing, it will be assigned as 31st. If AEs, Concomitant Medication and Medical History Month is missing, it will be assigned as 12.

For the PK analysis the following will be applied:

- For the concentration descriptive summaries, concentrations may be excluded if sampling time deviation is considered large to affect the profile at the discretion of the pharmacokineticist.
- Concentrations that are below limit of quantification (BLQ) prior to the first quantifiable value will be set equal to zero. Post dose BLQ concentrations, post T_{\max} , will be set to missing.

- c. Where there are no results (NR), these will be set to missing.
- d. If more than 75% of values per nominal timepoint and treatment group are BLQ, then all descriptive statistics, except for nBLQ, will be denoted as not calculable (NC).
- e. For the calculation and graphical representation (semi-log and log-log plots) of geometric descriptive statistics, 0 values will be set to missing.

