- f. For the purpose of calculating the non-compartmental PK parameters, concentrations that are BLQ prior to the first quantifiable value will be set equal to zero. BLQ values after measurable concentrations will be set to missing. Concentrations in the terminal phase, which is preceded by two BLQ values, will be set to zero.
- g. For the calculation of summary statistics of PK parameters, all NR and NC values in a data series will be set to missing.

Conversion of categorical values

In some instances, continuous variables are expressed as a range (i.e., < 10). In such cases, values may be converted to the range boundary (upper or lower limit as applicable). As an example, a value of <10 may be converted to 10. Such substitutions will be clearly documented in the footnotes of relevant outputs.

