 CVN766 5 mg, CVN766 15 mg, CVN766 45 mg (Fasted), CVN766 45 mg (Fed) CVN766 125 mg, CVN766 250 mg, Overall CVN766, Overall Placebo, Placebo (Fed) and Overall.

Table 14.1.4.1 Summary of Medical History MAD(Safety Population)

Programing Note:
Same as Table 14.1.4.1
Source Listing: 16.2.4.2.2
Add following treatment columns;
CVN766 45 mg, CVN766 125 mg, CVN766 250 mg, Overall CVN766, Overall Placebo and Overall.

Table 14.2.1.1 Summary of Plasma Concentrations (ng/mL) of CVN766 SAD (PK Population)

Analyte:xxx

Treatment	Visit	Timepoints	n	nBLQ	Mean	SD	CV%	Median	Minimum	Maximum	Geometric Mean	Geometric CV%
CVN766 5 mg (N=xx)	Day 1	Pre-dose	xx	xx	xx.x	xx.x	xx.x	xx.x	xx	xx	xx.x	xx.x
		1h										
		1.5h	xx	xx	xx.x	xx.x	xx.x	xx.x	xx	xx	xx.x	xx.x
		2h	xx	xx	xx.x	xx.x	xx.x	xx.x	xx	xx	xx.x	xx.x
		3h	xx	xx	xx.x	xx.x	xx.x	xx.x	xx	xx	xx.x	xx.x
		5h	xx	xx	xx.x	xx.x	xx.x	xx.x	xx	xx	xx.x	xx.x
		8h	xx	xx	xx.x	xx.x	xx.x	xx.x	xx	xx	xx.x	xx.x
		12h	xx	xx	xx.x	xx.x	xx.x	xx.x	xx	xx	xx.x	xx.x
		16h	xx	xx	xx.x	xx.x	xx.x	xx.x	xx	xx	xx.x	xx.x
		Day 2	24h	xx	xx	xx.x	xx.x	xx.x	xx.x	xx	xx	xx.x
36h	xx		xx	xx.x	xx.x	xx.x	xx.x	xx	xx	xx.x	xx.x	
Day 3	48h	xx	xx	xx.x	xx.x	xx.x	xx.x	xx	xx	xx.x	xx.x	
Day 4	72h	xx	xx	xx.x	xx.x	xx.x	xx.x	xx	xx	xx.x	xx.x	
CVN766 15 mg (N=xx)	Day 1	Pre-dose	xx	xx	xx.x	xx.x	xx.x	xx.x	xx	xx	xx.x	xx.x

Source Listing: 16.2.6.1.1

BLQ = Below Limit of Quantitation; CV% = Coefficient of Variation; SD = Standard Deviation.

BLQ is set as 0 for standard statistics (such as arithmetic mean), and set as missing for geometric statistics.

Programing Note:

Add following treatment rows;

CVN766 5 mg, CVN766 15 mg, CVN766 45 mg (Fasted), CVN766 45 mg (Fed), CVN766 125 mg, CVN766 250 mg.

Table 14.2.1.2 Summary of Plasma Concentrations (ng/mL) of CVN766 MAD (PK Population)

Analyte:xxx

Treatment	Visit	Timepoint	n	nBLQ	Mean	SD	CV%	Median	Minimum	Maximum	Geometric Mean	Geometric CV%
CVN766 45 mg (N=xx)	Day 1	Pre-dose	xx	xx	xx.x	xx.x	xx.x	xx.x	xx	xx	xx.x	xx.x
		0.5h										
		1h										
		1.5h										
			...									
	Day 2	24h	xx	xx	xx.x	xx.x	xx.x	xx.x	xx	xx	xx.x	xx.x
	Day 3	Pre-dose	xx	xx	xx.x	xx.x	xx.x	xx.x	xx	xx	xx.x	xx.x
	Day 4	Pre-dose	xx	xx	xx.x	xx.x	xx.x	xx.x	xx	xx	xx.x	xx.x
	Day 5	Pre-dose	xx	xx	xx.x	xx.x	xx.x	xx.x	xx	xx	xx.x	xx.x
	Day 6	Pre-dose	xx	xx	xx.x	xx.x	xx.x	xx.x	xx	xx	xx.x	xx.x
	Day 7	Pre-dose	xx	xx	xx.x	xx.x	xx.x	xx.x	xx	xx	xx.x	xx.x
		0.5h										
		1h										
		...										
Day 8	24h	xx	xx	xx.x	xx.x	xx.x	xx.x	xx	xx	xx.x	xx.x	

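### SAP 3.5 and 10.7 give different rules for BLQ concentrations in the arithmetic summaries and, more narrowly, in the NCA, and neither takes precedence

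*SAP*

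**What the plan says.** **Concentration summaries.** In section 3.5, PK item (b), BLQ concentrations "prior to the first quantifiable value will be set equal to zero. Post dose BLQ concentrations" falling after T_max then become missing. Section 10.7, under its summary of PK concentrations, has no time restriction: BLQ values "will be set to 0 for the calculation of standard statistics (i.e. arithmetic mean) and set to missing for the calculation of geometric statistics". The footnote of mock Table 14.2.1.1 agrees with 10.7: "BLQ is set as 0 for standard statistics (such as arithmetic mean), and set as missing for geometric statistics". The same footnote stands under the MAD plasma, CSF and urine concentration shells. Item (d) of 3.5 makes the statistics not calculable only when more than 75% of the values at a time point are BLQ.

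**Urine.** Both the Part 2 introduction in 10.5 and section 10.6 send BLQ handling of urine concentrations to 3.5. The urine shell (Table 14.2.3.1) carries the zero rule.

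**NCA.** Item (f) of 3.5 sets BLQ to zero before the first quantifiable value and to missing afterwards, then adds: "Concentrations in the terminal phase, which is preceded by two BLQ values, will be set to zero". Section 10.7, under its summary of plasma PK parameters, sets embedded BLQ to missing and continues: "Concentrations that are BLQ in the terminal phase after the last measurable concentration will be set to missing". It has no two-BLQ clause. The preceding part of 10.7 says that values before the first measurable one are set to BLQ, where 3.5(f) and the later part of 10.7 say zero.

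**Precedence.** None is stated. Section 10.7 does note that the imputation for NCA differs from the one for summaries.

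**The concern.** A programmer who follows 3.5 and one who follows 10.7 will report different arithmetic means and SDs from the same concentrations, and each can cite the SAP. The effect falls on late sampling times and troughs, where BLQ values are most likely.

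Troughs matter because 10.5 judges attainment of steady state by eye from mean C_trough. A trough lies after the T_max of the preceding dose, so 3.5(b) would drop a BLQ trough. If early troughs are BLQ in some subjects and later ones are not, dropping them raises the early means and can hide accumulation.

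The NCA discrepancy bears on individual AUC_t and T_last, and possibly AUC_inf, but only for an unusual profile.

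**Working it through.** The SAP gives no figure to reproduce, and no LLOQ, variability or expected BLQ share. The size is therefore shown as a range.

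**Inputs.** Active subjects per cohort: n = 6 (SAD, 2.1.1: "6 subjects will receive a single oral dose of CVN766 suspension"; MAD, 2.1.2: "6 subjects will receive a daily oral dose of CVN766"). NC threshold: more than 75% BLQ (3.5(d)).

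**Step 1: gap between the two summary rules.** Let k of n post-T_max values be BLQ and S be the sum of the measurable values. Under 3.5(b) the mean is S/(n − k). Under 10.7 it is S/n. The ratio is n/(n − k), whatever the concentrations are.

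| BLQ of 6 | Share | Ratio, missing to zero |
|---|---|---|
| 1 | 16.7% | 6/5 = 1.20 |
| 2 | 33.3% | 6/4 = 1.50 |
| 3 | 50.0% | 6/3 = 2.00 |
| 4 | 66.7% | 6/2 = 3.00 |
| 5 | 83.3% | NC, above 75% |

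Invented values 2, 3 and 4 with three BLQ give 9/3 = 3.0 under 3.5(b) and 9/6 = 1.5 under 10.7. If these were early troughs, and later troughs had no BLQ and a mean of 3.0, the trough plot would be flat under one rule and show a doubling under the other.

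**Step 2: each rule against the true mean.** Assume log-normal concentrations with between-subject CV from 30% to 100% and BLQ share p. With σ² = ln(1 + CV²) and z_p the normal quantile of p, zero/true = Φ(σ − z_p) and missing/true = Φ(σ − z_p)/(1 − p). Example with CV 50% and p = 0.5: σ = √ln 1.25 = 0.472 and Φ(0.472) = 0.68, so the zero rule gives 0.68 of the true mean and the missing rule 0.68/0.5 = 1.36. Over the CV range:

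| BLQ share | Missing/true | Zero/true |
|---|---|---|
| 1/6 | 1.08–1.16 | 0.90–0.96 |
| 2/6 | 1.15–1.34 | 0.77–0.90 |
| 3/6 | 1.23–1.60 | 0.62–0.80 |
| 4/6 | 1.34–1.97 | 0.45–0.66 |

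Both rules are biased, in opposite directions.

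**Step 3: geometric statistics.** No conflict arises. After T_max, BLQ is missing under both sections, and 3.5(e) also turns early zeros into missing.

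**Step 4: NCA.** For ordinary BLQ values after the first measurable one, 3.5(f) and both parts of 10.7 agree on missing. They part only when a measurable value follows two BLQ values. Take an invented profile on the SAP sampling times: 0, 20, 60, 80, 75, 60, 40, 25, 14, 8 and 3 from 0 to 24 h, BLQ at 36 and 48 h, and 1.2 at 72 h. The linear trapezoid to 24 h gives 529.75. If the 72 h value is kept, it adds (3 + 1.2)/2 × 48 = 100.8, for a total of 630.55. AUC_t differs by 100.8/529.75 = 19%, and T_last is 72 h or 24 h. AUC_inf may also move, because C_last and the points available for λ_z change.

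**The case against.** The intended summary rule can largely be inferred. Section 10.7 and the shells agree with each other, and 10.7 says that NCA and summary imputation differ, which fits the zero rule. Item 3.5(b) names no purpose and nearly duplicates the NCA rule, so its second sentence looks like a stray. The tables show n and nBLQ, the summaries are descriptive, and the primary endpoints are safety. All of that limits the consequence. It does not remove the conflict: (b) stands between (a), on descriptive concentration summaries, and (d), on descriptive statistics, while NCA has its own item (f). For urine, 10.5 and 10.6 point expressly to 3.5.

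On NCA, 10.7 is silent on a measurable value after two BLQ values, and 3.5(f) could be read as a special case added to it. That reading is fair, and it is why this part is the lesser one. The two texts still need to say the same thing.

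A reader might also infer three stronger claims that the SAP does not support:

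- That the missing rule inflates late means two- to three-fold. That is the ratio between the rules at 3 or 4 BLQ of 6. Against the true mean, the overstatement stayed below two-fold in every scenario in step 2.
- That the summary rule distorts the dose-proportionality slope. The power model in 3.3 is fitted to individual PK parameters, which the summary imputation never enters.
- That the 75% threshold is wrong for geometric means. The sections agree on geometric statistics, and a stricter cut-off would be a preference.

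**Conclusion.** The contradiction is real and should be removed. For arithmetic concentration summaries after T_max, the SAP gives two rules whose means differ by a factor of 1.2 to 3.0 at n = 6 with 1 to 4 BLQ values. The ratio is exact and needs no distributional assumption, but it assumes that all six active subjects contribute; with fewer, the factor for a given number of BLQ values is larger. How often it will matter is unknown, because the SAP gives no LLOQ or expected BLQ share. The bias figures rest on the assumed log-normal model with CV 30–100%.

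The main practical consequence is for mean concentration curves and the visual steady-state judgement. The NCA discrepancy is narrower: AUC_t, T_last and possibly AUC_inf change only for a profile with a measurable value after two BLQ values. The 19% is an illustration, not an expected size.

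**What to change.** Before unblinding, put one rule per purpose in 3.5.

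- **Summaries:** BLQ as zero for arithmetic statistics and as missing for geometric statistics, at all times; delete the post-T_max sentence of 3.5(b). This choice matches 10.7, the shells and the note in 10.7 that NCA handling differs. It is chosen for consistency, not because zero is unbiased.
- **NCA:** BLQ before the first measurable value as zero and BLQ after it as missing, with one stated handling of a measurable value that follows two consecutive BLQ values. Delete the wording in 10.7 that sets early values to BLQ.
- **Cross-references:** have 10.7, the urine text in 10.5 and 10.6, and the shell footnotes refer to 3.5 instead of restating the rules.

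The cost is SAP wording. With the zero rule kept, the summary footnotes in the shells already say the right thing.
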